## 10.0 COMPANION STUDIES

There will be 1 mandatory imaging companion for patients whose disease is being monitored by MRI. There will also be 2 optional sub-studies: A091105-HO1 (Health Outcomes) and A091105-ST1 (Correlative Science). A091105-HO1 and A091105-ST-1 must be offered to all patients for their consent, although patient participation is optional.

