### 10.3.4 A091105-ST1 Biopsies

#### Pre- and day 8 (+ 7 days) post-randomization biopsy guidelines

A091105-ST1 must be offered to all patients enrolled on A091105 (although patients may opt to not participate). Patients who consent to A091105-ST1 will undergo 2 biopsies (pre-treatment and day 8 post-randomization).

The following exploratory studies will be performed and analyzed in the laboratory of [name], correlative chair. Bio-informatics analysis will be provided by MSKCC Bio-informatics core lab. Blood, pre-treatment and day 8 matched tumor biopsies are required elements of this study for patients. Patients will undergo 2 biopsies (procuring 5 cores for each biopsy) by interventional radiology under image guided CT or U/S. Core biopsies will be evaluated for the following studies: 1) one core will be formalin fixed for pathological studies and TMA construction, 2) 1 - 2 cores will be used for gene array expression profiling to determine a sorafenib signature of response, whole exome sequencing, microRNA array and epigenetics 3) one core will be used for a constrained evaluation of phospho-proteomic changes utilizing a Zaptosens reverse protein array of selected pathways identified from genetic studies.

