### 15.3.3 Statistical design for correlative study A091105-ST1

See the note in [Section 15.2](#), which will apply to all analyses for this section A091105-ST1.

Statistics for Core #1: Archival FFPE and TMA studies: Associations among the possible predictors of response to sorafenib and CTNNB1 mutations will be examined using Fisher’s exact test, Kruskal-Wallis test, or Spearman’s correlation coefficient as appropriate. Variables considered include *CTNNB1* genotype, tumor size, tumor site, gender, age at initial diagnosis, and primary versus recurrent disease. Strata will be compared by using the log-rank test. Multivariate models will be constructed by introducing all variables aforementioned simultaneously into the model and then eliminating variables using the backward selection method. *P* values will be two-tailed and considered significant at alpha 0.05. Analyses will be conducted using SAS for Windows (release 9.3; SAS Institute, Cary, NC).

Statistics for Core #2: Microarray: A two-sided t-test will be used to identify differentially expressed genes on log transformed data and those with a twofold change. False discovery rate (FDR) will be assessed by permutation testing ( $n = 1000$ ) of the sample group labels. The selection approach is to first compute two *t*-tests and fold changes for each comparison between pre-treatment and day 8 versus the normal skin biopsy. Genes that have a nominal *p* value < 0.01 and fold > 2 for each comparison will be selected. To assess FDR,

permutation testing of the same selection will be performed 1000 times and the sample group labels switched around in each permutation. Java TreeView color maps will be generated. To unravel a treatment-specific gene expression signature, the analysis will identify over- and under-expressed genes in pre- treatment and day 8 biopsies as compared to all control samples (germlineDNA extracted from whole blood). Using Sigterms, sorafenib associated gene signature will search for Gene Ontology (GO) annotation terms, gene sets curated by the Molecular Signature Database (MSigDB, v2.5 and top enriched transcription factor sequence motifs. Enrichment will be assessed by one-sided Fisher's exact test with estimated FDR.

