Statistics for Core #3 and 4: For each paired sample, differences in protein levels will be compared by paired t-test. This sample size of 75 patients will allow 93% power to detect 1 standardized difference. Quantitative changes in IHC score of VEGF, PDGFR and  $\beta$ -catenin cytoplasm/nuclear ratio will be correlated with disease status at 1 year by Fishers exact test.

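### A091105-ST1: the stated 93% power for 75 patients does not follow from the paired t-test named, and the expression-array plan uses germline DNA as comparator without specifying a day 8 versus pre-treatment contrast

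*Combined protocol and SAP*

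**What the plan says.** **Protein analysis (15.3.3, Core #3 and 4).** The test is "For each paired sample, differences in protein levels will be compared by paired t-test", followed by "This sample size of 75 patients will allow 93% power to detect 1 standardized difference". This paragraph gives no alpha and does not say which SD standardizes the difference.

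**Who is biopsied.** Section 15.1.1 gives 75 as the number to be randomized, 50 to sorafenib and 25 to placebo. Section 10.0 says the two sub-studies "must be offered to all patients for their consent, although patient participation is optional". Section 6.3.2 adds that biopsies are done in consenting patients when safe and feasible. Section 10.3.1 says that all patients will be biopsied, under a heading marked optional.

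**Expression arrays (15.3.3, Core #2).** The t-tests and "fold changes for each comparison between pre-treatment and day 8 versus the normal skin biopsy" come first. The treatment-specific signature is then sought from genes over- or under-expressed in the pre-treatment and day 8 biopsies "as compared to all control samples (germlineDNA extracted from whole blood". Section 10.3.4 says the array is run on total RNA isolated from tissue. Sections 10.3.1 and 10.3.3 put the aim as treatment-induced change, studied in paired tumor biopsies.

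**The concern.** A power statement should let the reader recover the test, the sample and the error rate. Here the test named and the power quoted cannot both be right for 75 pairs, and 75 is not a number of pairs that the plan gives any reason to expect. A reader therefore cannot tell whether within-patient change or a comparison between arms was powered. The two behave very differently if participation is low.

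The array plan has a more basic difficulty. DNA carries no expression level, so one named comparison cannot be carried out. The contrast that would show change on treatment is not written down. Patients give two research biopsies of five cores each for this work, so its analysis should be executable as described.

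**Working it through.** **Inputs.** From Section 15.3.3: paired t-test, n = 75, effect d = 1, stated power 93%. From Section 15.1.1: 50 sorafenib, 25 placebo. Assumed: two-sided alpha 0.05, with d in SDs of the paired difference. Numbers of pairs below 75 are also assumptions, because the plan gives no participation rate.

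**1. The plan's figure under its own test.** Paired power is the chance that a noncentral t with n − 1 degrees of freedom and noncentrality d√n exceeds the critical value.
- n = 75: √75 = 8.66 against a critical value of about 1.99. Power is above 99.99%, so 93% is not reproduced.
- n = 14: √14 = 3.74 against 2.16. Power is 93.2%; 13 pairs give 91.1%.
- n = 75 with power fixed at 93%: the detectable effect is d = 0.402.

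**2. Could another paired reading give 93%?**
- Stricter alpha (0.01, 0.001, 0.05/300): power stays above 99.9% at 75 pairs.
- Effect standardized by the SD at one time point: the SD of the difference is σ√(2(1 − ρ)). With ρ = 0, d = 1/√2 = 0.71 and power is at least 99.99%. With ρ = −0.9, d = 1/√3.8 = 0.51 and power is 99.2%.
- Pooling 50 sorafenib pairs (mean change 1 SD) with 25 placebo pairs (no change): mean 50/75 = 0.667, SD √(1 + (2/3)(1/3)) = 1.106, d = 0.603. Simulated power is 99.98% at 0.05 and 99.7% at 0.01.

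None of these returns 93%.

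**3. Between-group tests.** The noncentrality is d/√(1/n₁ + 1/n₂).
- 25 v 25: 1/√0.08 = 3.54. Two-sided 0.05 gives 93.4% (t).
- 50 v 25: 1/√0.06 = 4.082. Two-sided 0.01 gives Φ(4.082 − 2.576) = 93.4% (normal) or 92.1% (t). Two-sided 0.05 gives 98.1% (t).

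Two different designs come close to 93%, so the origin cannot be recovered.

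**4. What realistic numbers would give** (d = 1, two-sided 0.05, per protein, unadjusted):

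| Paired test, pairs | Power | Between arms on change | Power |
|---|---|---|---|
| 10 | 80% | 10 v 5 | 39% |
| 14 | 93% | 20 v 10 | 70% |
| 20 | 99% | 50 v 25 | 98% |
| 25 | 99.8% | | |

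Low participation costs the paired test little and the between-arm test a great deal. That is why the comparison must be named.

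**5. Array plan, set side by side.** The array measures tissue RNA (10.3.4), but the comparator for the signature is blood DNA (15.3.3). Section 10.3.4 also lists blood DNA as normal-tissue control for the nucleic-acid work; that is sound for sequencing but not for expression. The comparisons written out set pre-treatment and day 8 against normal skin or against blood DNA. The opening Core #2 sentence names a two-sided t-test but no groups. No sentence sets day 8 against pre-treatment within patient.

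**6. Permutation.** The plan says "permutation testing of the same selection will be performed 1000 times and the sample group labels switched around in each permutation". For paired data the labels should be exchanged within patient, that is, the sign of each difference flipped. Flipping every sign leaves |t| unchanged, so n pairs give 2^(n − 1) distinct two-sided statistics: 512 for 10 pairs and 1,024 for 11.

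**The case against.** The strongest reply is that nothing is put at risk. The stated power is lower than 75 pairs would give, 14 pairs already reach 93% at 0.05, and the work is optional and exploratory. All of that stands, and it limits the weight of the point. It does not make the statement correct, and it does not help if a between-arm comparison was meant.

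Four stronger readings are tempting but not supported:

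- A reader might infer that the calculation was 50 v 25 at 0.01, because the gene rule uses "value < 0.01 and fold > 2 for each comparison will be selected". But 25 v 25 at 0.05 fits as well, and the protein paragraph does not refer to 0.01.
- A reader might infer that some 300 proteins will be tested, which under Bonferroni would cut power at 14 pairs to 17%. Section 10.3.4 gives over 300 as the antibodies available. It describes the evaluation as constrained to selected pathways and names those of interest. The number to be tested is open, and no multiplicity rule is stated; that is missing detail, not evidence of low power.
- A reader might infer that no treatment contrast is intended for expression. Sections 2.3.2 and 10.3.1 say treatment-induced changes will be quantified, so the contrast may well be intended. What can be said is that Section 15.3.3 does not specify it.
- A reader might infer from the specimen table in Section 6.3 that the normal skin cannot be obtained. That table lists trial specimens, and the skin may come from outside the trial. Only its source is unstated.

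**Conclusion.** The point holds. The 93% does not follow from a paired t-test on 75 patients: that test gives more than 99.99% at two-sided 0.05, and 93% matches 14 pairs at 1 SD or 0.40 SD at 75 pairs. The documents do not show which calculation was meant. The 75 is the full randomized sample, including 25 placebo patients, and not an expected number of biopsy pairs. By contrast, the quality-of-life sub-study in Section 15.3.2 does state an expected evaluable share (about 70%) and works from 51 patients. In the array plan, the germline DNA comparison cannot be done, and the within-patient contrast is unspecified.

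The power figures rest on an assumed alpha and, unless stated otherwise, on the SD of the paired difference; the mismatch survives every paired variant tried. It would be wrong to conclude that the protein analysis is underpowered. The effect is limited to an optional exploratory sub-study, and progression-free survival and the Section 15.2 endpoints are untouched. It deserves correction because a stated power and a stated analysis rule are wrong as written and cheap to put right.

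**What to change.** 1. **Section 15.3.3, Core #3 and 4.** Name the comparison that the power refers to, the alpha, the SD definition and the actual or expected number of patients with both biopsies, and restate the power. If paired, the wording could be: two-sided paired t-test at 0.05, per protein and unadjusted, 1 SD being the SD of the paired difference; 10, 14, 20 or 25 pairs give 80%, 93%, 99% or 99.8% power. If between arms on change: 10 v 5, 20 v 10 or 50 v 25 give 39%, 70% or 98%. Any multiplicity adjustment should use the number of proteins actually tested, not the antibody catalogue. The current text post-dates the November 2017 unblinding, so the actual number of pairs may already be known.
2. **Section 15.3.3, Core #2.** Remove germline DNA as the expression comparator and keep it as the normal control for sequencing.
3. **Section 15.3.3, Core #2.** Add the within-patient day 8 minus pre-treatment change as the expression contrast, with a paired test and sign-flip permutation (11 pairs for at least 1,000 distinct two-sided statistics). Report it by arm, with the between-arm comparison of change where numbers allow, since change within one arm cannot separate drug from time or repeat-biopsy effects.
4. **Minor wording.** State the source of the normal skin RNA, and align Section 10.3.1 with the optional status of the sub-study.

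The cost is text in Section 15.3.3 and one sentence in Section 10.3.1. The stated ST1 sample will probably be smaller than 75. No new samples, visits or patients are needed.

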### **Core #5**

Biopsies will be descriptive and comment on 1) proliferation (Ki-67 expressed as percentage) to assess treatment response (pre-treatment base line and post therapy for drug effect) and expressed as percentage of tumor cells as <10%, 10-25%, 25-50% and >50%, 2) degree of fibrosis, 3) changes in vascularity, 4) necrosis and 5) ratio of nuclear to cytoplasmic beta catenin.

For TMA construction, the techniques are previously well described by Lazar and colleagues. Hematoxylin and eosin (H&E) stained sections will be reviewed to define areas of desmoid tumor; dermal scars, reactive tissue and solitary fibrous tumor will serve as controls. Using an automated TMA apparatus (ATA-27; Beecher Instruments, Sun Prairie, WI), 0.6-mm punch samples (two per case) will be obtained along with controls and formatted into three recipient blocks. H&E-staining of 4-micron TMA sections will be used to verify all samples.

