Immunohistochemistry: The polymeric biotin-free horseradish peroxidase method on a Microsystems Bond Max stainer (Beecher Instruments, Bannockburn, IL) will be used for immunohistochemistry. Four-micron-thick sections will be prepared from formalin-fixed paraffin-embedded tissue blocks and dried in a 60-degree oven for 20 minutes. Sections will be placed in the automated Bond Max stainer, pretreated with enzyme-induced epitope retrieval for 2 minutes followed by incubation with antibodies against beta-catenin (BD Biosciences, San Jose, CA), midkine (Antigenix America, NY), MMP2 (Chemicon, MA) and ADAM12 (Abcam, MA). Additional antibodies may be utilized to interrogate specific pathways identified in micro-array work. Anti-mouse secondary antibody and the Refine polymer detection kit (Leica) will be used for immunostaining, with 3,3-diaminobenzidine serving as chromagen. Positive and negative controls will run in parallel. Labeling intensity grading will be performed by soft tissue pathologist ([name]) as none (\_0), weak (\_1), moderate (\_2), or strong (\_3). For the ratio of cellular to nuclear beta catenins, the percentage of positive tumor cells will be estimated from the two paired TMA samples for each case. For nuclear staining, weak (\_1) will be defined functionally as having to view nuclei at X400 to confirm nuclear accumulation. Moderate (\_2) staining could be viewed at X200 and the blue hematoxylin nuclear counterstain. In strong (\_3) staining, the nuclear counterstain will no longer be visible in the majority of nuclei. The staining on the entire array will be performed in the MSKCC clinical immunohistochemistry facility on two occasions and each scored independently.

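### In the optional ST1 substudy, the immunohistochemistry analysis in Section 15.3.3 does not match the stains and the beta-catenin ratio described in Section 10.3.4

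*Combined protocol and SAP*

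**What the plan says.** Section 15.3.3, in the paragraph on Core #3 and 4, names three immunohistochemistry (IHC) parameters: "Quantitative changes in IHC score of VEGF, PDGFR and" the beta-catenin ratio. It continues that the "cytoplasm/nuclear ratio will be correlated with disease status at 1 year by Fishers exact test". It gives no cut-point and does not say how many levels disease status has.

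The IHC methods are in Section 10.3.4 under Core #5. Sections undergo "incubation with antibodies against beta-catenin (BD Biosciences, San Jose, CA), midkine (Antigenix America, NY), MMP2 (Chemicon, MA) and ADAM12 (Abcam, MA"). A further sentence leaves room for more: "Additional antibodies may be utilized to interrogate specific pathways identified in micro-array work".

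Core #5 describes the beta-catenin measure twice. The list of pathology readings has the "ratio of nuclear to cytoplasmic beta catenin". The IHC paragraph says: "For the ratio of cellular to nuclear beta catenins, the percentage of positive tumor cells will be estimated from the two paired TMA samples". The same paragraph grades labeling intensity on a four-step scale from none (0) to strong (3).

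VEGFR2/3 and PDGFR-beta do appear in Section 10.3.4, but under Core #3 and #4, as targets of the reverse protein array run on tissue lysate.

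**The concern.** An analyst who follows Section 10.3.4 will hold no IHC score for VEGF or PDGFR, yet Section 15.3.3 asks for both. For the third parameter, the analyst must choose between ratio forms that point in opposite directions. The form in the statistical section puts nuclear staining in the denominator. Section 10.3.3 links nuclear accumulation of beta-catenin to activation of growth signals, so complete loss of nuclear staining after treatment is a result that the substudy should be able to record. The test needs categories, and none are set for the ratio. Each gap leaves a choice to be made after the data are seen, in material for which consenting patients undergo two research biopsies.

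**Working it through.** The documents give no sample size, power or significance level specific to the IHC parameters, so there is no planned figure to reproduce. The 93% power in the same paragraph of Section 15.3.3 belongs to the paired t-test of protein levels. The check is a comparison of the texts, plus simple arithmetic on the ratio.

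**Step 1: markers.**

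| Parameter analysed in 15.3.3 | Named IHC antibody in 10.3.4, Core #5? | Elsewhere in 10.3.4 |
|---|---|---|
| VEGF | No | Receptors VEGFR2/3 on the protein array; the ligand is in no assay list |
| PDGFR | No | PDGFR-beta on the protein array |
| Beta-catenin ratio | Yes (beta-catenin) | – |

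One of three parameters has a named stain. The array gives a signal from lysate, which is not an IHC score and does not locate staining within the cell.

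**Step 2: direction of the ratio.**

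| Place | Form |
|---|---|
| 10.3.4, Core #5, pathology readings | nuclear / cytoplasmic (N/C) |
| 10.3.4, Core #5, IHC paragraph | cellular / nuclear; cellular is not defined and need not mean cytoplasmic |
| 15.3.3 | cytoplasmic / nuclear (C/N) |

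The percentages below are illustrative and are not from the documents. Baseline is 40% cytoplasmic-positive and 80% nuclear-positive cells.

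- Follow-up at 80% and 40%: C/N goes from 40/80 = 0.5 to 80/40 = 2.0. N/C goes from 2.0 to 0.5. The sign of the change reverses.
- Write r1 and r2 for C/N before and after. The change in N/C is 1/r2 − 1/r1 = −(r2 − r1)/(r1·r2). When both components are non-zero, the two forms carry the same direction with labels swapped. The size of the change does not convert by a fixed factor, because it depends on r1 and r2. A cut-point on the size of change therefore has to name the form it applies to.

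**Step 3: zero nuclear staining.** With follow-up at 80% cytoplasmic and 0% nuclear, C/N = 80/0 has no value, whereas N/C = 0/80 = 0. The percentage of nuclear-positive cells simply goes from 80 to 0, a change of −80 points. No rule in the documents covers a zero denominator.

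**Step 4: test.** Fisher's exact test works on counts in categories. A change in a 0–3 intensity grade already falls into steps from −3 to +3, so it could be tabulated without a cut. A change in a ratio of percentages could not. The missing cut-point therefore concerns the beta-catenin ratio specifically.

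**The case against.** The best defence is that this is one sentence about an optional substudy whose assays are labelled exploratory, and that the sentence itself shows an intention to stain for VEGF and PDGFR. The clause on additional antibodies permits that. C/N and N/C are reciprocals, so an increase/decrease classification gives the same two-sided Fisher p-value either way when neither component is zero. All of this stands, and it limits the point to a mismatch that can be reconciled. It does not remove the mismatch: the antibody clause is permissive, names no marker and is tied to microarray results, and reciprocity fails at zero.

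Several stronger readings are tempting, and the documents do not support them.

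- *Loss of nuclear staining would bias the association toward no effect.* Nothing says how often nuclear positivity reaches 0% or that such specimens would be excluded. A patient going from positive to 0% could be placed in the largest-increase category of C/N; only a zero at baseline, or zero in both compartments, is unclear. Counting zeros on the 0–3 intensity scale does not help, because Section 10.3.4 builds the ratio from percentages of positive cells.
- *Fisher's test costs a known share of efficiency.* That would require a specified split of a variable with a known distribution, and the plan gives neither.
- *Midkine, MMP2 and ADAM12 are stained without any analysis.* The Core #1 paragraph of Section 15.3.3 covers archival and tissue-microarray studies with an open list of variables, and Core #5 describes the biopsy readings as descriptive. Coverage is vague, but not shown to be absent.
- *Section 10.3.3 makes nuclear beta-catenin the central pathway.* It gives the mechanism as background and does not rank pathways.

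**Conclusion.** The point holds as an inconsistency between Sections 10.3.4 and 15.3.3 with three parts. First, two of the three IHC parameters to be analysed have no named stain. Second, the beta-catenin ratio is given in three forms; the one in the statistical section runs opposite to the first form in Core #5 and is undefined at 0% nuclear-positive cells. Third, a quantitative change in that ratio is to be tested with a categorical test and no cut-point.

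A reader might infer that the endpoints cannot be obtained at all. That goes too far: extra staining is allowed, and the ratio conflict can be settled by choosing one form. How many specimens the zero denominator would affect cannot be estimated from the documents. The conclusion rests only on the text of the two sections and on reading the ratio as one of percentages, as the IHC paragraph indicates. It is worth correcting because the correction is nearly free. The consequence is confined to ST1; the primary and secondary endpoints do not depend on it.

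**What to change.** 1. Make Sections 10.3.4 and 15.3.3 name the same markers. The cheapest way is to delete VEGF and PDGFR IHC from Section 15.3.3 and use the changes in VEGFR2/3 and PDGFR-beta from the protein array already planned. This gives up VEGF itself, which is in no assay list. If IHC for VEGF and PDGFR is wanted, add both to the antibody list, at the cost of two more stains.
2. In all three places, define the beta-catenin measure as the percentage of nuclear-positive tumor cells, which is defined at zero. A proportion such as N/(N + C) would still fail when both are zero.
3. Replace Fisher's exact test for this measure with a rank test of the paired change (day 8 minus pre-treatment) across disease status at 1 year: Wilcoxon rank-sum if status is set at two levels, Kruskal-Wallis if more. State the levels; the response table in Section 13.4.4 has more than two. The Core #1 paragraph of Section 15.3.3 already allows Kruskal-Wallis, so this fits the existing plan.

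The cost is wording in two sections, with no new patient or biopsy. The downside is that the cytoplasmic component leaves the main IHC measure; it can be reported descriptively.

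### Section 15.3.3 tests quantitative IHC changes against 1-year disease status with Fisher's exact test only; a rank test would use the ordering, need no cut-point and usually have more power

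*Combined protocol and SAP*

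**What the plan says.** Section 15.3.3, under Core #3 and 4, describes the variables as "Quantitative changes in IHC score of VEGF, PDGFR and" the beta-catenin cytoplasm/nuclear ratio, and says that they "will be correlated with disease status at 1 year by Fishers exact test". No other test is offered for them. The same paragraph gives a power figure, "This sample size of 75 patients will allow 93% power to detect 1 standardized difference", but it follows the paired t-test for protein levels. No power is given for the IHC analysis.

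The scales are described in section 10.3.4 under Core #5. Staining intensity is graded in four steps, none to strong, scored 0 to 3: "Labeling intensity grading will be performed by soft tissue pathologist". For the beta-catenin ratio, "the percentage of positive tumor cells will be estimated from the two paired TMA samples for each case". Neither place says how a change should be grouped.

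Rank methods do appear in section 15.3.3 ("Kruskal-Wallis test, or Spearman"), but only for Core #1. Disease status at 1 year is not defined there. Section 15.2.4 uses the term disease status for RECIST v1.1 classification, whose overall categories in section 13.4.4 include CR, PR, SD and PD.

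**The concern.** The test does not match the type of variable. A near-continuous ratio cannot enter Fisher's test until someone decides where to cut it, and the plan leaves that decision open. An ordered score can enter uncut, but the test then treats its levels as unordered labels. Either way information is given up, in a substudy that may be small: "Patients who consent to A091105-ST1 will undergo 2 biopsies", and consent is optional. A true link between a marker change and outcome is then easier to miss, and the result for the ratio depends on an unrecorded choice by the analyst.

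**Working it through.** **The only stated power figure.** It is 93% for 75 patients and 1 standardized difference, placed with the paired t-test. With 75 pairs the noncentrality is √75 × 1 = 8.66, and 8.66 − 1.96 = 6.70, so two-sided power exceeds 99.99%. A two-sample comparison of 50 with 25 gives 98.1%. About 93% arises with 14 pairs (93.2%) or 25 vs 25 (93.4%). The figure does not reproduce at 75 patients, but that is a separate matter and gives no support to the Fisher analysis.

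**Inputs from the plan.** 50 sorafenib and 25 placebo patients, with median PFS of 15 and 6 months (section 15.1.1). Two-sided 0.05 is stated for Core #1 ("values will be two-tailed and considered significant at alpha 0.05") and assumed to carry over.

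**Inputs assumed.** Normal changes with shift d (in SDs) between two status groups; 20 to 75 patients with paired samples; the position of the cut.

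**Status split at 75 patients, if PFS is exponential.** Progression-free at 12 months: 0.5^(12/15) = 0.574 on sorafenib and 0.5^(12/6) = 0.25 on placebo. Then 50 × 0.574 + 25 × 0.25 ≈ 35 progression-free and 40 not.

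**Ratio, after a cut.** Wilcoxon rank-sum power against Fisher power, 6,000 simulated data sets per cell. Each entry is at the d (from 0.4 to 1.2) with the largest loss; losses were taken before rounding.

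| Patients (split) | Cut at pooled median | Cut at midpoint | Cut 1 SD off-centre |
|---|---|---|---|
| 75 (40/35) | 69.5 vs 53.4%, loss 16 | 68.8 vs 47.9%, loss 21 | loss 41 |
| 51 (27/24) | 65.7 vs 45.3%, loss 20 | 76.9 vs 53.6%, loss 23 | loss 40 |
| 50 (21/29) | 75.8 vs 45.5%, loss 30 | 74.4 vs 54.9%, loss 19 | loss 45 |
| 38 (20/18) | 82.2 vs 53.9%, loss 28 | 74.0 vs 51.9%, loss 22 | loss 39 |
| 25 (13/12) | 78.2 vs 54.0%, loss 24 | 78.6 vs 62.7%, loss 16 | loss 39 |
| 20 (11/9) | 67.4 vs 23.4%, loss 44 | 67.9 vs 39.2%, loss 29 | loss 43 |

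Losses are smaller where both tests have high power. At 75 patients and d = 1 the figures are 98.6 vs 93.1% (median cut) and 98.5 vs 90.3% (midpoint cut), a loss of 5 to 8 points. Equal groups at d = 1 with a median cut give 52 vs 30% (10/10), 71 vs 47% (15/15) and 86 vs 62% (20/20).

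With an odd total, the middle patient must be put on one side of a median cut. At 40/35 that choice alone moves Fisher's power at d = 0.6 from 53% to 44% (rank-sum about 70%), and at d = 1 from 93% to 89%.

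**VEGF and PDGFR, uncut.** A 0-3 grade gives a change from −3 to +3. The exact test on the k × 2 table uses P = ∏ C(c_j, a_j) / C(N, n₁), where c_j is the number of patients at level j and a_j the number of those in the first status group. Reordering the levels leaves this product unchanged, so the ordering plays no part. Simulated with a four-level change score, this test loses about 3 to 21 points against the tie-corrected Wilcoxon test: for example 66.1 vs 45.4% (25/25, d = 0.7) and 99.1 vs 96.0% (37/38, d = 1.1).

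**The case against.** The strongest reply is that little depends on this. Section 10.3.4 calls the studies exploratory, and no decision, alpha or sample size rests on the sentence. Fisher's test is a valid test of association, and at 75 patients with a 1-SD difference a central cut costs few points. All of that stands, and it sets the weight of the point.

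A reader might also infer more than the documents support:

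- **That a cut-point is forced for all three markers.** The 0-3 grades allow an uncut exact test for VEGF and PDGFR. Carrying that grade over to them is itself an assumption, because Core #5 names other antibodies. Only the ratio clearly needs a grouping rule.
- **That most of the information is lost.** Under a normal shift a median split keeps 2/π ≈ 64% of the t-test's efficiency, and (2/π)/(3/π) = two thirds of Wilcoxon's.
- **That the false-positive rate is inflated.** Taking the best of five cut-points would raise it to about 8.6% (20 vs 20) or 11.6% (25 vs 15). Nothing in the plan proposes this, and a natural split such as decreased or not could be set without looking at the data.
- **That the rank-sum test is automatically the replacement.** It needs two outcome groups, and the plan does not say that 1-year status is binary.

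**Conclusion.** The point holds as a low-cost improvement. The plan names a categorical test for changes that it calls quantitative, gives no grouping rule for the one marker that needs it, and would ignore the ordering of the other two. A rank test is the better choice.

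Under normal shifts and a central cut, the loss is roughly 5 to 30 points over the sizes and effects considered. It reaches 44 points in one 20-patient configuration and 39 to 45 points with a cut 1 SD off-centre, and it shrinks towards zero where both tests have very low or very high power. It would be tempting to quote a single figure, such as 25 points, as the most that can be lost. The documents give no IHC effect size, number of paired samples, cut-point or status split, so the range is illustrative and no figure in it is a bound. The primary endpoint and its analysis are unaffected.

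**What to change.** In section 15.3.3, Core #3 and 4:

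1. Define disease status at 1 year.
2. Replace Fisher's test for these three markers with a rank test on the day 8 minus pre-treatment change. If status is progressed or not, use the Wilcoxon rank-sum test, exact or tie-corrected. If several or ordered RECIST categories are kept, use Kruskal-Wallis or Spearman, both already named for Core #1.
3. Keep Fisher's test for truly categorical markers. If it is kept for the ratio, state the cut-point before analysis, including the side on which a value equal to the cut falls.

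The cost is a line or two of text. No new data, samples or assays are needed.
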